## 1. Background Information

### 1.1 Name, Description and Intended Use of the Product for Investigation

Orthodontic aligners have been commercially available since 1998 with the introduction of Invisalign® Aligners that are an aesthetic alternative for orthodontic treatment. 3M Oral Care Solutions Division plans to expand the orthodontic aesthetic solutions portfolio by offering customized 3M Clear Aligners for orthodontic treatment.

The 3M™ Clear Aligner System is a series of clear lightweight plastic appliances (aligners) indicated for the treatment of tooth malocclusions in patients with permanent dentition (i.e. all second molars). By utilizing a series of incremental tooth movements, (torque, tipping, rotation, bodily movements such as intrusion and extrusion) the 3M Clear Aligners sequentially re-position teeth by way of continuous gentle force.

The 3M Clear Aligner System may include attachments and/or buttons, which offer a solution for patients, who want an aesthetic treatment with a set of removable clear aligners that correct tooth malocclusions without the use of conventional wire and bracket orthodontic technology.

### 1.2 Risk/Benefit Summary

#### 1.2.1 Risks

Listed below are the potential and known risks with wearing the 3M Clear Aligners:

- Gastrointestinal tract obstruction resulting from aligner fragments due to aligner breakage, attachment and button debond.
- Aspiration of 3M Clear Aligner fragments resulting from breakage, attachment, button debond.
- Aspiration of attachment or buttons resulting from breakage or bond failure.
- Choking due to 3M Clear Aligner fragments resulting from breakage.
- Choking due to attachment or buttons resulting from breakage or bond failure.
- Gingival tissue and teeth may become sore and tender after initial aligner placement and when placing each sequential 3M Clear Aligner.
- Speech may be affected when initially beginning treatment but should be minimized in 2 weeks after beginning aligner therapy.
- Gums, cheeks, and lips may be abraded or irritated by the 3M Clear Aligners, attachments or buttons
- Swollen and inflamed gums or tongue while wearing the 3M Clear Aligners.
- Enamel damage due to hard debris in aligner or due to removal of tight aligner.
- Staining of teeth due to poor hygiene, food debris in 3M Clear Aligner, or consumption of sugary liquids, or beverages that may cause stains on teeth, i.e. coffee, wine.

3M Confidential

Document Name: CLIN-PROT-ICH-US-05-300635

Clinical and Non-Clinical: CLIN-INDEX-3M-SPON-US-05-013821, Clinical and Non-Clinical: CLIN-INDEX-3M-SPON-US-11-050005

- Caries, decalcification periodontaldisease and permanent stains may occur if consistent and proper oral hygiene such as brushing and flossing are not performed as recommended.
- Decalcification, and periodontal disease caused by eating and/or drinking sugary foods and beverages while wearing the 3M Clear Aligner.
- Tooth root damage due to tooth movement too fast or beyond bond while wearing the 3M Clear Aligner.
- The bite may change during the course of treatment resulting in temporary discomfort.
- The bite may require additional adjustments at the end of treatment.
- Temporary increase in salivation or dryness of mouth may occur.
- Temporal-mandibular joint (TMJ) pain, headaches or ear problems may occur.
- Existing dental restorations may become dislodged while removal of tight aligner.
- Failure to wear the appliance for the prescribed number of hours per day or in the prescribed order and/or not using the 3M Clear Aligner as directed may lengthen the treatment time and affect the final treatment outcome.
- Relapse of teeth after treatment due to the failure of not wearing the retainers.
- Attachment debonds which will require rebonding the attachment during an additional appointment
- Button debonds require rebonding the attachment during an additional appointment
- Aligners may become damaged
- Redness, swelling to gums, lips, due to sensitization to attachment composite material
- Toxicity from exposure to uncured attachment material.
- Cuts to gingiva, tongue, lips due to sharp or rough surface of attachment material.
- Respiratory tract irritation due to finishing/polishing dust or removal of attachment remnant material.

### 1.2.2 Benefits

The individual receives treatment for correcting tooth malocclusions, while wearing the 3M Clear Aligner instead of conventional wire and bracket orthodontic technology. Indirectly, subjects may benefit from the additional clinical attention.

### 1.3 Material Application

The subjects will undergo a target of up to 18 months of treatment to align the teeth to the planned target. The investigator will receive 6 sets of 3M Clear Aligners per shipment from 3M and will then provide each subject with 3 sets at each 6-week follow up appointment. The subject will wear the 3M Clear Aligners for at least 22 hours per day, with the exception of consumption of meals and beverages, with the exception of water, which can be consumed while wearing the aligners. During each 6-week period between follow up visits, subjects will wear

3M Confidential

Document Name: CLIN-PROT-ICH-US-05-300635

Clinical and Non-Clinical: CLIN-INDEX-3M-SPON-US-05-013821, Clinical and Non-Clinical: CLIN-INDEX-3M-SPON-US-11-050005

each set of 3M Clear Aligners for 2 weeks, in the order indicated per the Orthodontists treatment plan.

## **1.4 Good Clinical Practice (GCP) and Regulatory Requirements**

The 3M™ Clear Aligner System is categorized as a Class II, medical device subject to 510(k) clearance. The 3M Aligner system has been cleared for use by the Federal Drug Administration. This study will be conducted in compliance with this protocol and Good Clinical Practice (GCP).

## **1.5 Study Population**

The subject population for this study will be male and female subjects  $\geq 14$  years of age. There will be no attempt to enroll equal number of male and female subjects. Subjects who meet the inclusion and exclusion criteria will be asked to participate in the study. Up to a total of 180 subjects may be enrolled at up to 12 different clinical research sites, (up to 15 subjects per site).

## **2. Study Purpose and Objectives**

The purpose of this study is to evaluate the safety and efficacy of the 3M Clear Aligners along with the use of attachments and/or buttons for the treatment of tooth malocclusions.

### **2.1 Primary Objective**

The primary objective of this study is to evaluate the efficacy of 3M Clear Aligners to correct tooth malocclusions with the use of attachments and/or buttons, as determined by the amount of teeth movement and overall achievement goals of the treatment plan.

### **2.2 Secondary Objectives**

The secondary objectives of this study are:

- Evaluate safety.
- Evaluate individual tooth movements per recommended treatment ranges.
- Evaluate length of treatment time for different malocclusions.
- Evaluate the use of attachments and attachment bond failures when used with 3M aligners.
- Evaluate orthodontist satisfaction with treatment outcome and use of 3M aligners.
- Evaluate orthodontist satisfaction with the Treatment Management Portal Software.
- Evaluate subject satisfaction with the overall treatment of the 3M Clear Aligners, especially regarding ease of insertion and removal, aesthetics (discoloration), ease of cleaning and subject compliance while wearing the aligners.
- Evaluate number of mid-course corrections or refinements needed.
- Evaluate digital scans to predict tooth movement for future product development.

3M Confidential

Document Name: CLIN-PROT-ICH-US-05-300635

Clinical and Non-Clinical: CLIN-INDEX-3M-SPON-US-05-013821, Clinical and Non-Clinical: CLIN-INDEX-3M-SPON-US-11-050005

### **3. Study Design**

#### **3.1 Study Type**

This is a prospective, multi-center study with a targeted duration of 18 months, to assess the safety and efficacy of 3M Clear Aligners, with the use of attachments to correct teeth malocclusions.

#### **3.2 Primary and Secondary Endpoints**

##### **3.2.1 Primary Endpoint**

The primary endpoint is the percent of subjects who have achieved correction of tooth malocclusions with use of 3M Clear Aligners. The successful correction of the malocclusion will be based on the subject's achievement of the target setup or the treatment plan as judged by the Orthodontist.

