#### **3.3 Randomization and Blinding**

This is a single intervention schedule study so no randomization or blinding will occur. Subjects who meet the inclusion and exclusion criteria and are willing to sign an informed consent, will be asked to participate in the study.

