### 3.6 Study Duration

The expected duration of subject participation may be 6 to 24 months, even though the maximum targeted duration is 18 months. The duration could be extended due to mid-course corrections or refinements, as determined by the Investigator. The subject is expected to attend study visits at 6-week intervals for the duration of the study. Study visits may range from a minimum of 7 to 18 scheduled visits, dependent on the duration indicated per the investigators treatment plan for each subject. Additional visits may be scheduled per Investigator discretion.

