## 5. Treatment of Subjects

### 5.1 Schedule of Treatments

The 3M Aligner System includes a series of aligners that offer a solution for patients who want an aesthetic treatment with a set of removable aligners to correct tooth malocclusions without the use of conventional wire and bracket orthodontic technology. The 3M Clear Aligners are being studied in a manner consistent with their intended use.

The Principal Investigators will treat subjects requiring correction of tooth malocclusions using the 3M Clear Aligners with attachments and/or buttons as necessary for additional force applied to teeth or to help with tooth movement.

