## 7. Assessment of Efficacy

Efficacy of the 3M Clear Aligners for each subject will be based on the assessment by the investigator that teeth correction is progressing as expected at each orthodontic visit, and that the subject's teeth have reached the final target set-up by the end of treatment.

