### 9.1.2 Analysis of Primary Endpoint

The primary endpoint is the proportion of subjects achieving treatment success or attainment of teeth movements targets of the final set-up. It is possible for the final set-up to be modified mid-treatment or to be refined at the end of treatment, and thus success of the aligner will be based on the last or most relevant final set-up. Primary endpoint will be ascertained at the end of active 3M Clear Aligner wear (before retainer use). Subjects missing their primary endpoint assessment (e.g., subjects lost to follow-up) will be assumed to be treatment failures. The two-sided 95% confidence interval of this proportion will be computed using the Wilson score method. Documentation of subjects excluded from either the FAS or PP datasets for the computation of success rate will be justified and documented prior to datalock.

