### 9.1.3 Analysis of Secondary endpoints

In general, the reported summary statistics for continuous measures will include number, mean, standard deviation, median and range. Reported summary statistics for categorical measures will include number and frequency.

Summaries of the overall percent completion or accuracy per subject will be summarized overall and for those categorized under treatment success or failure. Percent completion or percent accuracy will involve comparison of the final tooth positions relative to the planned or targeted positions against pre-treatment or baseline positions.

In addition, individual teeth movement and the malocclusions resolved in this study will be summarized as appropriate.

The secondary endpoints of treatment compliance, percent comfort and percent satisfaction will be summarized for various performance parameters.

Furthermore, summaries of attachment use, button use, and possible bond failures will be presented. In addition, occurrence of mid-course corrections and refinements will be summarized.

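### The primary success rate rests on the unblinded treating orthodontist's judgement, has three different definitions and no stated tolerance, and lacks a pre-specified scan-based check

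*Combined protocol and SAP*

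**What the plan says.** Section 3.2.1 bases success on the subject's "achievement of the target setup or the treatment plan as judged by the Orthodontist". Section 7 makes efficacy for each subject "based on the assessment by the investigator that teeth correction is progressing as expected at each orthodontic visit", and adds that the final set-up must be reached by the end of treatment. Section 9.1.2 restates the endpoint as treatment success or "attainment of teeth movements targets of the final set-up". It allows the set-up to be changed during treatment or refined at the end, and scores against the latest set-up or whichever is considered most relevant.

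On who judges, Section 5.1 states: "The Principal Investigators will treat subjects requiring correction of tooth malocclusions". Section 3.3 states: "This is a single intervention schedule study so no randomization or blinding will occur".

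On timing, Section 9.1.2 reads the endpoint at the end of active aligner wear, before retainers. Section 3.6 targets at most 18 months, expects 6 to 24, and adds: "The duration could be extended due to mid-course corrections or refinements, as determined by the Investigator".

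On measurement, scans are taken at the initial, follow-up and final visits (Sections 5.1.2 to 5.1.4). Section 9.1.3 plans a per-subject percent completion or accuracy, a "comparison of the final tooth positions relative to the planned or targeted positions against pre-treatment or baseline positions". It is summarised overall and by judged success or failure, and it does not define success.

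**The concern.** The study has one arm and one primary number. With no comparator, lenient judging cannot cancel between groups and passes straight into the reported proportion. The Wilson interval covers sampling error only, so it would look equally precise whether or not the judgement was generous.

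Three features leave room for leniency: no tolerance says how close is close enough, the definitions are not the same, and the target itself may be replaced. The primary objective (Section 2.1) refers to the amount of tooth movement, which the scans can measure, yet no success rate is planned from them.

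**Working it through.** **1. The three definitions side by side**

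| Section | What counts as success | Assessor | Tolerance |
|---|---|---|---|
| 3.2.1 | Target set-up *or* treatment plan achieved | Orthodontist | None |
| 7 | On course at each visit *and* final set-up reached | Investigator | None |
| 9.1.2 | Movement targets of the latest or most relevant set-up attained | Not named | None |

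Two subjects show that these differ:

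- Subject A is judged off course at one visit but reaches the final set-up. A passes under 9.1.2 and, read literally, fails under 7.
- Subject B fulfils the treatment plan in the orthodontist's view but misses a movement target of the set-up. B passes under 3.2.1 and fails under 9.1.2.

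**2. The reference and the clock**

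Under Section 5.2.6, a mid-course correction or refinement means a new order and approval of a new target set-up. Section 9.1.2 then allows scoring against that newer set-up. The investigator who judges success therefore also approves the target. Section 9.1.3 does not say which set-up percent accuracy uses.

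Section 3.6 foresees 7 to 18 scheduled visits at 6-week intervals. Eighteen visits span 17 × 6 = 102 weeks, in line with the 24-month upper expectation. Success after month 18 counts the same as success before it, and no planned analysis separates the two.

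**3. Sensitivity of the rate (illustration)**

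The documents give no expected success rate and no scan threshold, so *t* and *f* below are assumptions.

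- *n* = 180, the enrolment ceiling (Sections 1.5 and 9.2; 12 sites × 15 subjects).
- *t* = assumed proportion meeting a scan criterion.
- *f* = assumed share of scan misses judged a success. Every scan success is taken to be judged a success.
- Judged rate = *t* + (1 − *t*) × *f*.

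For *t* = 0.70:

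| *f* | Judged rate | Count of 180 | Wilson 95% interval |
|---|---|---|---|
| 10% | 0.70 + 0.30 × 0.10 = 73.0% | 131 | 65.9 to 78.8% |
| 25% | 0.70 + 0.30 × 0.25 = 77.5% | 139 | 70.6 to 82.7% |
| 50% | 0.70 + 0.30 × 0.50 = 85.0% | 153 | 79.1 to 89.5% |

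Counts are rounded to whole subjects. The smallest *f* at which the interval lies wholly above *t*:

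| *t* | Smallest *f* | Judged rate |
|---|---|---|
| 60% | 17.9% | 0.60 + 0.40 × 0.179 = 67.2% |
| 70% | 22.4% | 0.70 + 0.30 × 0.224 = 76.7% |
| 80% | 29.3% | 0.80 + 0.20 × 0.293 = 85.9% |

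**4. Allowing error in the other direction**

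If orthodontists also fail a share *g* of scan successes, the net shift is (1 − *t*)*f* − *tg*. At *t* = 0.70 and *f* = 0.25 it is zero when *g* = 0.075 / 0.70 = 10.7%. Neither the sign nor the size of the shift can be read from the plan. Only a cross-tabulation of judged against scan-based success would show it.

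**The case against.** The strongest reply is that the construct is correction of malocclusion, which an orthodontist is qualified to judge. No document shows that a percent-accuracy cut-off measures it better. That stands: a scan threshold is another yardstick, not the truth, and replacing the primary endpoint is a debatable trade-off.

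Other parts of the reply also stand:

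- A reader might infer that success has no time limit. It has an event-based time point and an expected duration, and treatment times and refinement counts are secondary endpoints. Only a calendar cut-off is missing.
- A reader might infer that extension turns the rate into a measure of retention. The documents do not support this. Section 9 generally treats non-completion because of strongly anchored teeth as failure, and Section 9.1.2 counts missing assessments as failure. Counting success after refinement is an explicit choice.
- Section 9.1.3 already splits percent accuracy by judged success or failure, so a poor fit among judged successes would partly show. But it sets no criterion and gives no success rate.
- The study is descriptive, with no formal test (Section 9.3), on a cleared device. No pass or fail decision depends on the rate, but a descriptive efficacy estimate can still be biased.
- Section 9 refers to a Statistical Analysis Plan, and no separate SAP text is in the supplied document. A tolerance set there cannot be ruled out.

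**Conclusion.** The point holds as a SHOULD. Success is assessed by the unblinded treating clinician, no tolerance is stated, the three definitions conflict, and the reference set-up can move with that clinician's approval. The primary rate can be inflated without the interval showing it.

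The size is unknown. The figures above are assumed sensitivities at the full 180 subjects; a smaller sample would widen the interval and raise the share of misses needed to exclude the scan rate. A reader might infer that judged success is in fact biased upward, or that it must be dropped as primary. The documents support neither. They support reconciling the wording and adding a check from data already collected. Scoring scans only against the last approved set-up would not be enough, because a redrawn target would still be met on scan.

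**What to change.** 1. Use one success definition in Sections 3.2.1, 7 and 9.1.2. Name the reference set-up and remove the choice between the latest and the most relevant one. State the assessor and the tolerance.
2. Keep the orthodontist's judgement as primary if the sponsor prefers. Pre-specify as the key supportive analysis a scan-based success rate: final scan against set-up, with a numerical percent-accuracy or residual-deviation threshold. Fix the threshold and the superimposition method in the SAP before any outcome scans are analysed, including for an interim summary.
3. Compute that rate against both the originally approved and the last approved set-up, with missing counted as failure and a Wilson interval. The two set-ups coincide for subjects whose set-up was never revised, so any gap between the rates shows the effect of revised targets.
4. Cross-tabulate scan-based with judged success, extending the Section 9.1.3 summary.
5. Report the proportion successful by 18 months from first aligner, and the proportion successful without a mid-course correction or refinement. Section 3.8 already records dates of use, and corrections and refinements are already counted.

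Cost: protocol and SAP wording plus some analysis work, with no added visit or scan. A threshold and method must be chosen in advance, across several scanner systems, and someone must run the superimposition. Final scans may be missing for withdrawn subjects, because Section 3.7.2 asks for withdrawal assessments only where possible. The supportive rates may be less favourable than the judged rate.

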##### **3.2.2 Secondary Endpoints**

- Safety of 3M Clear Aligners as evaluated by the number of unanticipated adverse events.
- Summary of individual tooth movement and total arch movements, for example, tooth rotations, tooth intrusions/extrusions, and arch space closures.
- Summary of treatment times for different tooth malocclusions
- Summary of the total number of aligners used, treatment duration and use of attachments, buttons, and bond failures.
- Percent satisfaction of orthodontists with treatment outcome.
- Percent satisfaction of orthodontist with the 3M Treatment Management Portal software.
- Percent satisfaction of subject with overall treatment when using 3M Clear Aligners, such as: (aligner comfort, pain during wear, ease of insertion, ease of removal, ease of cleaning and satisfaction with aesthetics).
- Summary of the number of mid-course corrections or refinements needed.

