## 8. Assessment of Safety

### 8.1 Safety Parameters

The primary measures of safety will be evaluated by the incidence of adverse events reported during the study.

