### 8.2 Adverse Events

The Investigator is responsible for identifying adverse events that occur to each subject throughout the study and follow-up period. An adverse event can occur at any time during the conduct of the study, in any phase of the study or after the study is completed. An adverse event can be identified by the Investigator or reported by the subject.

Note: The Federal Privacy Rule (HIPAA) specifically permits the use and disclosure of protected health information “without written authorization of the individual” when used for public health activities such as reporting adverse events, tracking FDA-related products, enabling recalls, repairs, replacements, lookbacks, or conducting post-market surveillance [45 CFR 164.512]. This use and disclosure is subject to the *minimum necessary* standard, i.e. “the minimum necessary to accomplish the intended use, disclosure, or request” [45 CFR 164.502(b)(1)].

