#### Definitions

- Adverse event (AE) means any undesirable clinical occurrence in a subject whether or not it is considered to be device or drug related.
- Device-related adverse event (adverse device effect) is an AE considered by the Investigator to have a reasonable likelihood of being associated with the treatment device.
- Serious adverse device effect is a device effect that has a serious adverse effect on health or safety causing hospitalization or prolonged hospitalization, or is life threatening or causes death.
- Adverse drug experience is an AE that is considered by the Investigator to have a reasonable likelihood of being associated with the treatment drug.
- Serious adverse drug experience is an adverse drug experience that is fatal or life-threatening, requires inpatient hospitalization or prolongation of existing hospitalization, a persistent or significant disability/incapacity, or results in a congenital anomaly/birth defect.
- An Unanticipated Adverse Device Effect (UADE) means any serious adverse effect on health or safety or any life-threatening problem or death caused by or associated with a

3M Confidential

Document Name: CLIN-PROT-ICH-US-05-300635

Clinical and Non-Clinical: CLIN-INDEX-3M-SPON-US-05-013821, Clinical and Non-Clinical: CLIN-INDEX-3M-SPON-US-11-050005

device, if that effect, problem or death was not previously identified in nature, severity or degree of incidence in the Protocol or application (including a supplementary plan or application), or any other unanticipated serious problem associated with a device that relates to the rights, safety, or welfare of subjects.

All adverse events will be followed until they are resolved or for 30 days after the subject's participation in the study ends.

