## Recording and Reporting

The Investigator records each material-related adverse event on an Adverse Device Effect Record. Documentation includes the description, severity, seriousness, date of onset and resolution, relationship to the treatment material, action taken and outcome.

The Investigator must promptly report an adverse device effect to the 3M study monitor. If the adverse device effect is also considered by the Investigator to be serious and/or unanticipated, the Investigator must report it to the IRB as soon as possible and within IRB requirements.

A serious AE involving a non-3M commercialized product is reported to the 3M study monitor and IRB of record.

If a subject has no adverse device effect during the study, the absence of such must be recorded on the CRF.

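### Section 3.2.2 measures safety by an undefined count of unanticipated events, section 8.1 by adverse-event incidence, and complete all-cause recording is not assured

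*Combined protocol and SAP*

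**What the plan says.** Evaluating safety is the first secondary objective in section 2.2. Two sections then say how it will be measured.

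- Section 3.2.2: "Safety of 3M Clear Aligners as evaluated by the number of unanticipated adverse events".
- Section 8.1: "The primary measures of safety will be evaluated by the incidence of adverse events reported during the study".

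Section 8.2 defines the event broadly: "Adverse event (AE) means any undesirable clinical occurrence in a subject whether or not it is considered to be device or drug related". It also defines adverse device effects, serious adverse device effects, the corresponding drug terms and the unanticipated adverse device effect (UADE). It does not define an unanticipated adverse event. A UADE must be serious, and the effect must be one that "was not previously identified in nature, severity or degree of incidence in the Protocol or application". The reporting rule in the same section joins the two ideas differently: "If the adverse device effect is also considered by the Investigator to be serious and/or unanticipated", the investigator reports it to the IRB.

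On capture, section 8.2 says: "The Investigator is responsible for identifying adverse events that occur to each subject throughout the study and follow-up period". It also says: "All adverse events will be followed until they are resolved or for 30 days after" participation ends. The explicit recording instruction is narrower: "The Investigator records each material-related adverse event on an Adverse Device Effect Record". The only negative entry required on the case report form (CRF) is for the absence of an adverse device effect.

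Section 9.1.3 gives a general rule for categorical summaries but does not name AEs. Section 9 refers to a SAP. No separate SAP text and no CRFs were available for this review.

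**The concern.** The two safety measures differ in which events qualify (unanticipated or all) and in metric (a number or an incidence). One report could present both, but nothing in the protocol says so, or says which one answers the safety objective.

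The narrower measure also works against its purpose. The better a harm is known in advance, the less likely it is to count. A report that relied on this 3.2.2 bullet for its safety conclusion could state zero events although harms described in 1.2.1 had occurred; a report following 8.1 would show them. Section 9.3 allows an interim look at safety that may lead to stopping, so the ambiguity could reach a decision as well as a table.

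The 8.1 measure has its own weakness. If unrelated AEs are written down at some of the up to 12 sites and not at others, the incidence depends partly on each investigator's view of causality.

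**Working it through.** The plan states no safety figure to reproduce, so the check is mainly textual.

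1. **Meaning of the 3.2.2 term.** If it means UADE, only serious effects or problems qualify. If it takes its meaning from the reporting rule in 8.2, where an effect may be serious, unanticipated or both, a non-serious unanticipated effect qualifies too. The two readings can give different counts; they do so whenever a non-serious unanticipated effect occurs.

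2. **Effect of the risk list.** Section 1.2.1 has 28 bullets. Each names a risk by its nature; none gives an expected rate. Five concern the airway or gut: gastrointestinal obstruction, aspiration (two bullets) and choking (two bullets). On either reading, a listed harm is generally not unanticipated. The UADE definition has an exception for severity or degree of incidence beyond what was identified. For these five, 1.2.1 states neither, so there is no reference against which to apply the exception. A serious aspiration could be argued in or out of the count.

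3. **How a zero would read.** This is for illustration, since the 3.2.2 endpoint is a number and not a proportion. Section 9.1.2 uses the Wilson method for the primary endpoint. With no events, its upper 95% limit is z²/(n + z²), with z² = 3.84. At the full 180 subjects this is 3.84/183.84 = 2.1%. At an assumed enrolment of 90 it is 3.84/93.84 = 4.1%. Either would look reassuring, yet a zero on this count puts no bound on how many subjects had a listed harm.

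4. **Precision of the 8.1 measure.** The Wilson interval is widest at 50%, where 90/180 gives 42.8% to 57.2%. The 50% is the worst case for precision, not an expected rate. The broader measure can be estimated at the planned size.

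5. **Capture.** Three steps in 8.2 can be compared:
   - identification: AEs in each subject, through the study and follow-up period;
   - follow-up: all AEs;
   - recording and negative entry: material-related events and device effects only.

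   Section 10 lets the monitor inspect AEs that have been documented, and 13.6 requires AE reports to be kept. Section 8.2 also has a reporting rule for serious AEs involving a commercial product from another manufacturer. None of these requires every AE to be recorded. Without a negative entry for any AE, a blank cannot be told apart from no event.

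**The case against.** The strongest reply is that the protocol covers more than the one bullet suggests. Other 3.2.2 bullets report bond failures, comfort and pain during wear. Soft tissue is assessed at every follow-up visit and at the final visit (5.1.3, 5.1.4). Any device-related event, including aspiration or choking on an aligner part, must be recorded and promptly reported to the study monitor under 8.2, with severity, seriousness and relationship to the material documented. The device already has FDA clearance, the study is single-arm and descriptive, and device-focused recording is a defensible choice.

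All of this stands, and it limits the point. A reader might infer that serious listed harms would go unrecorded or are plainly excluded from the endpoint. The documents do not support that: such events are recorded, and their classification is ambiguous. A reader might also infer that unrelated AEs are not collected. The identification and follow-up duties point the other way, and a general AE form or AE table may exist in CRFs or a SAP not seen here. Nor is the counting period wholly missing, since 8.1 refers to events reported during the study and 8.2 sets an identification period. Finally, the 28 bullets are not 28 harms to subjects; they include damaged aligners, debonds and longer treatment from poor wear.

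What the reply does not answer is the mismatch itself. The endpoint is undefined and differs from 8.1, and no section reconciles them.

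**Conclusion.** The concern holds as a mismatch between 3.2.2 and 8.1, together with a recording rule narrower than the AE definition that 8.1 relies on. It should be fixed. A zero under 3.2.2 would not show that the harms listed in 1.2.1 were absent. The number of events that would be missed cannot be computed, because the documents give no AE or attribution rates.

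Confidence is high for the mismatch, which rests on the protocol text alone. It is moderate for the recording gap, which assumes that the unseen CRFs and any separate SAP do not already require every AE to be recorded. The supportable statement there is that complete all-cause incidence is not assured, not that it will be missing.

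**What to change.** 1. In 3.2.2, state the safety endpoint as the number and percent of subjects with at least one AE, matching 8.1. Use subjects who wore at least one set of aligners, which is the full analysis set already defined in section 9.
2. Report adverse device effects, serious adverse device effects and UADEs as subsets. These terms are defined in 8.2; a general serious-AE category would need a new definition, because 8.2 defines seriousness only for device and drug effects.
3. Name this summary in 9.1.3.
4. In 8.2, extend the existing record, which already holds relationship to the treatment material, to every AE, and widen the negative entry to the absence of any AE.
5. State when the follow-up period in 8.2 ends for counting purposes.

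If the sponsor intends device-focused capture, the narrower alternative is to state the incidence of adverse device effects in both 8.1 and 3.2.2. That aligns the text but gives up all-cause incidence.

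The cost is wording in three sections and a change to CRF use. Recording would take place at the visits already scheduled (7 to 18 per subject under 3.6), with one added record per unrelated AE; the documents do not allow that number to be estimated. The downside is more AE recording and higher reported event counts. The primary efficacy analysis is unaffected.
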